### 5.1.2 Screening

After an individual has consented to participate in the study and informed is signed, that individual will be given a unique Screening Number manually created by the investigator. The subject's unique Screening Number will be documented in the Screening and Enrolment log. The eligibility of the subject will be determined based on the inclusion and exclusion criteria listed in section 4.0, Selection of Study Population and evaluated during this screening procedure.

Prior to study enrolment, demographic data will be collected from the subject, including: age, sex, race, height, weight and ethnicity. Medical history will also be collected, including but not limited to any medical history that may be relevant to subject eligibility for study participation such as prior vaccinations, concomitant medications, and previous and ongoing illnesses or injuries. Relevant medical history can also include any medical history that contributes to the understanding of an adverse event that occurs during study

participation, if it represents an exacerbation of an underlying disease/pre-existing problem.

Review of systems is a structured interview that queries the subject parent(s)/legal guardian(s) as to any complaints the subject has experienced across each organ system. This will be performed before enrolment and used to guide physical examination.

If applicable, prior and concomitant medications or vaccinations taken prior to start of study should be collected (refer to section 6.5, Prior and Concomitant Medications and Vaccines for further details).

Collect vital signs, including heart rate, temperature (this data is to be recorded in the source documents only). Vital signs measurements can be performed by a trained health care professional.

A general physical examination is to be performed by a qualified health care practitioner. "Qualified health care practitioner" refers to any licensed health care professional who is permitted by institutional policy to perform physical examinations and who is identified within the Study Staff Signature Log.

These data will be written in the source document (see section 9.1, Source Documentation). Should the physical assessment reveal any abnormal values or events, these must be documented in the CRF Adverse Events Form.

In the event that the individual is determined ineligible for study participation, he/she is considered a screen failure. The reason for screen failure must be documented in the Screening and Enrolment log. If the individual is determined to be eligible for the study, he/she will be enrolled into the study.

#### 5.1.3 Enrolment

After signing the informed consent form, if an individual is determined to be eligible for study participation, the investigator will enroll the subject and enter the Screening Number into the EDC system.

#### 5.1.4 Randomization

This is a non-randomized study. Enrolled subjects will be manually assigned a unique Subject ID. The Subject ID will be the subject's unique identification number for all CRFs and associated study documentation that will be used for duration of the study. The Screening Number ceases to be used and remains in the Screening and Enrolment Log only.

Doc Number: 68901057

If for any reason, after enrolment the subject fails to undergo the study procedures, this is an Early Termination and the reason should be recorded in source document as specified in the Source Data Agreement. The information on these Early Termination subjects should be kept distinct in the source documentation from subjects who are screen failures, as described in section 5.1.2, Screening.

### 5.2 Vaccination Clinic Visit(s)

Vaccination will be performed on day 1, day 61, day 121 and day 301. For studies which have visits for concomitant vaccinations or treatments, see section 6.5, Prior and Concomitant Medications and Vaccines for those visit procedures.

After completing the pre-vaccination procedures on day 1, administer the vaccine to the subject according to the procedures described in section 6.3, Vaccine Preparation and Administration. Prior to administration of each vaccination, confirm that the subject is eligible for additional study vaccinations and does not meet any criteria for delaying additional study vaccinations as described in section 4.0, Selection of Study Population.

#### **5.2.1** Post-vaccination Procedures

The following post-vaccination procedures will be performed on day 1, day 61, day 121 and day 301.

After vaccination, the subject will be observed for at least 30 minutes including observation for, solicited adverse events, and body temperature measurement. Record all safety data collected during this time in the subject's source document.

A Subject Diary will be used in this study to document solicited adverse events. The Subject Diary is the only source for collection of these data; therefore, it is critical that the subject parent(s)/legal guardian(s) completes the Subject Diary correctly. The subject parent(s)/legal guardian(s) should be trained on how and when to complete each field of the Subject Diary.

The subject parent(s)/legal guardian(s) should be trained on how to measure local solicited adverse events and body temperature. The measurement of solicited local adverse events is to be performed using the ruler provided by the site.

The subject parent(s)/legal guardian(s)] should be instructed how to perform body temperature measurement using the thermometer provided by the site. If the subject feels unusually hot or cold during the day, the subject parent(s)/legal guardian(s) should check body temperature. If the subject has fever, the highest body temperature observed that day should be recorded in the Subject Diary.

Doc Number: 68901057

Subject Diary training should be directed at the individual(s) who will perform the measurements of adverse events and who will enter the information into the Subject Diary. This individual may not be the subject parent(s)/legal guardian(s), but if a person other than the subject parent(s)/legal guardian(s) enters information into the Subject Diary, this person's identity must be documented in the Subject Diary and in the subject's source record. Any individual that makes entries into the Subject Diary must receive training on completion of the Subject Diary at the time of the visit. This training must be documented in the subject's source record.

The site should schedule the next clinic visit with the subject parent(s)/legal guardian(s).

The subject parent(s)/legal guardian(s) should be reminded of the next planned study activity. The subject parent(s)/legal guardian(s) will be reminded to complete the Subject Diary and to contact the site if there are any questions, and to contact the site immediately (or as soon as the subject is medically stable) if the subject has a medical condition that leads to a hospitalization or an emergency room visit or to a visit to/by a doctor or is of concern.

#### **5.2.2** Post-vaccination Reminder Calls

Subject Diary reminder calls will be performed on day 3 after each vaccination. The purpose of this call is to remind the subject parent(s)/legal guardian(s) about completion of the Subject Diary. The call follows the Subject Diary Reminder Telephone Call Script provided to the site. The subject parent(s)/legal guardian(s) should be reminded to contact the site via the telephone number provided in the informed consent to discuss medical questions.

### 5.3 Post-vaccination Visit(s)

Post-vaccination visits will be performed on day 331 and on day 661.

### 5.3.1 Follow-up Clinic Visit(s)

During the follow-up clinic visit, the Subject Diary will be reviewed. No changes to the information recorded within the Subject Diary are permissible. For details on the Subject Diary see sections 3.4.2, Tools Used for Data Collection and 5.2.1, Post-vaccination Procedures. The subject parent(s)/legal guardian(s)] will be interviewed to determine if any unsolicited adverse events occurred and if any concomitant medications or vaccines were taken/received in the time since the last clinic visit. The healthcare professional reviewing these data will discuss the symptoms (if any) reported by the subject and will determine if any additional diagnoses and/or adverse events are present. Adverse events reported by the subject parent(s)/legal guardian(s) at this follow-up clinic visit must be

recorded in the subject's source document and on an Adverse Events CRF, as specified in section 7.1, Safety Assessment.

Perform a brief symptom-directed physical examination if necessary according to symptoms the subject has reported. This is a physical examination that will include an examination of organ systems that are relevant to the investigator based on review of the subject's reported adverse events, concomitant medication and body temperature. The physical assessment must be performed by the investigator or designee of the investigator, who is qualified to perform a physical assessment in accordance with their institutional policy. Corresponding information is documented in the subject's source document and CRF(s).

A blood sample will be collected at Visit 5 and Visit 6, as specified in section 3.5.

The site should schedule the next clinic visit (if applicable) with the subject and parent(s)/legal guardian(s).

The subject parent/legal guardian(s) will receive a written reminder of the next planned study activity. The subject parent(s)/legal guardian(s) will be reminded to complete the Subject Diary and to contact the site if there are any questions and to contact the site immediately (or as soon as the subject is medically stable) if the subject has a medical condition that leads to a hospitalization or an emergency room visit.

# 5.3.2 Safety Follow-up Calls

There are no safety follow up calls in this study.

#### 5.4 Unscheduled Visits

An unscheduled visit describes a non-routine study visit triggered by a specific event. These could include anticipated or unanticipated adverse events or interventions.

## 5.5 Study Termination Visit

The study termination visit will occur on day 661. The termination visit may be a clinic visit or a telephone call. The date of termination is the date of the last contact (clinic visit or telephone call) in which the subject's health status was assessed or, in cases where the subject does not agree to any further safety follow-up, it is the date consent is withdrawn. This date should be recorded on the termination CRF page. For visit procedures to be performed for a subject whose planned study participation ends prematurely, please see section 5.5.1, Early Termination Visit.

Doc Number: 68901057

At the clinic visit or during the telephone call, the following procedures will be performed:

- Review of the safety information that includes review of Subject Diary, review of systems, interview of subject parent(s)/legal guardian(s) to collect any medically attended adverse events, AEs leading to withdrawal, SAEs
- Interview of subject parent(s)/legal guardian(s) to collect concomitant medications/ vaccinations associated with the AEs listed above, Symptom-directed physical assessment is to be performed as needed (including measurement of vital signs, body temperature and a check of general appearance)
- Collection of the last blood sample as specified in section 3.5 and section 4.3.
- The site will review with the subject parent(s)/legal guardian(s) the plan of when information relating to the subject's participation in the study may be available (e.g., study results, treatment assignments). It will also be discussed how information relating to the subject's participation in the study will be shared with the subject's healthcare provider, if the subject parent(s)/legal guardian(s) chooses to share this information

The site will complete the termination CRF page and this will mark the completion of the subject's participation in the study.

# **5.5.1** Early Termination Visit

When a subject is withdrawn from treatment or withdraws from the study, the investigator will notify the Sponsor and, when possible, will perform the procedures listed below. The reason(s) for the early termination will be included in the subject's source documentation. If the Early Termination Visit is a telephone call, collect as much information as possible. Early Termination Visits include subjects who were enrolled but not treated.

At the clinic visit or during the telephone call, the following procedures will be performed:

- Review of the safety information that includes review of Subject Diary (if applicable), review of systems, interview of subject and/or parent(s)/legal guardian(s) to collect unsolicited adverse events occurring within 30 days of vaccination, medically attended adverse events, AEs leading to withdrawal, SAEs.
- Interview of subject and/or parent(s)/legal guardian(s) to collect concomitant medications/ vaccinations associated with the above AEs.
- Symptom-directed physical assessment is to be performed as needed (including measurement of vital signs, body temperature and a check of general appearance).

The site will review with the subject parent(s)/legal guardian(s) the plan of when information relating to the subject's participation in the study may be available (e.g., study results, treatment assignments). It will also be discussed how information relating to the subject's participation in the study will be shared with the subject's healthcare provider, if the subject parent(s)/legal guardian(s) chooses to share this information.

The site will complete the termination CRF page and this will mark the completion of the subject's participation in the study.

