Site staff will record the following selected safety measures in the EDC:

- Solicited local adverse events: Injection site erythema, injection site induration, injection site tenderness (from Day 1 to Day 7 after each Men ACWY vaccination)
- Solicited systemic adverse events: Change in eating habits, sleepiness, irritability, vomiting, diarrhea, fever (from Day 1 to Day 7 after each Men ACWY vaccination).
- Unsolicited Adverse Events: All medically-attended unsolicited AEs and AEs leading to premature withdrawal will be collected (From Day 1 of the study and orally during the last clinical visit)
- Serious AEs: All SAEs will be collected from day 1 to end of study. SAEs will be
  monitored until resolution and/or the cause is identified (if a SAE remains
  unresolved at study termination, a clinical assessment will be made by the
  investigator and the Novartis medical monitor to determine whether continued
  follow up of the SAE is warranted) Medications used to treat any medicallyattended AE and SAE will be collected from Day 1 of the study and during the
  last clinical visit
- Note that all medically-attended unsolicited AEs, AEs leading to premature withdraw and all the medication used to treat them, these data will be captured by interviewing the subject and/or subjects' parents/guardian (as applicable) during clinic visits.

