#### 8.0 STATISTICAL CONSIDERATIONS

# 8.1 Endpoints

# 8.1.1 Primary Endpoint(s)

# 8.1.1.1 Primary Safety Endpoint(s)

Safety of the study vaccine will be assessed in all subjects in terms of the frequency and percentage of reported adverse events (AEs) including:

- Any solicited AEs reported within 30 minutes after each vaccination;
- Solicited local (i.e. erythema, induration and tenderness) and systemic (i.e. change in eating habits, sleepiness, irritability, vomiting, diarrhea, and fever (body temperature ≥ 38°C (100.4°F)) AEs reported from Day 1 to Day 7 after each vaccination;
- All medically-attended unsolicited AEs reported from Day 1 to Visit 6 (24 months of age);
- AEs leading to premature withdrawal reported from Day 1 to Visit 6 (24 months of age);
- SAEs reported from Day 1 to Visit 6 (24 months of age);

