## **8.4.2.1.3** Analysis of Unsolicited Adverse Events

This analysis applies to all adverse events occurring during the study, judged either as probably related, possibly related, or not related to vaccination by the investigator, recorded in AE CRF, with a start date on or after the date of first vaccination. AE starting prior to the first vaccination will only be listed. The original verbatim terms used by investigators to identify adverse events in the CRFs will be mapped to preferred terms using the MedDRA dictionary. The adverse events will then be grouped by MedDRA preferred terms into frequency tables according to system organ class.

All reported adverse events, as well as adverse events judged by the investigator as at least possibly related to study vaccine, will be summarized according to system organ class and preferred term within system organ class. These summaries will be presented by vaccination group and by interval of study observation. When an adverse event occurs more than once for a subject, the maximal severity and strongest relationship to the vaccine group will be counted.

Separate summaries will be produced for the following categories:

- Serious adverse events
- Adverse events that are possibly or probably related to vaccine
- Adverse event leading to withdrawal
- Adverse events leading to a medically attended visit

Data listings of all adverse events will be provided by subject. In addition, adverse events in the categories above will be provided as listed data.

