#### 13.3 Unsolicited Adverse Events

The first-line analysis will use unsolicited adverse event data from all reporting sources combined. A second-line analysis will encompass the analysis of unsolicited adverse events by source (e.g. diary cards, medical records, study specific worksheet).

All the unsolicited adverse events occurring during the study, judged either as probably related, possibly related, or not related to vaccination by the investigator, will be recorded. The original verbatim terms used by investigators to identify adverse events in the CRFs will be mapped to preferred terms using the MedDRA dictionary. The unsolicited adverse events will then be grouped by MedDRA preferred terms into frequency tables according to system organ class. Adverse events judged by the investigator as at least possibly related to study vaccine will be summarized, according to system organ class and preferred term within system organ class. When an unsolicited adverse event occurs more than once for a subject, the maximal severity and strongest relationship to the vaccine group will be counted.

Only vaccine-emergent adverse events (see section 8.7 for definition) will be analyzed, i.e., excluding those after a subject has given informed consent but before vaccination. The selection of unsolicited adverse events and the assignment to time intervals will be done by day of onset and not by days ongoing/persisting.

The summaries will be presented by onset and will include frequency distributions of the different adverse events:

- Vaccination period 1: Onset between visit 1/day 1 and visit 2/day 61.
- Vaccination period 2: Onset between visit 2/day 61 and visit 3/day 121.
- Vaccination period 3: Onset between visit 3/day 121 and visit 4/day 301.
- Vaccination period 4: Onset between visit 4/day 301 and visit 6/day 661or study termination.
- Overall

The analysis of unsolicited adverse events comprises the following categories:

- Medically attended unsolicited adverse event.
- Possibly or probably related medically attended unsolicited adverse events.
- Unsolicited adverse events leading to death.
- Serious adverse events.
- Possibly or probably related serious adverse event.
- Unsolicited adverse events leading to premature withdrawal from study.
- Unsolicited adverse events leading to dose reduction, interruption or delay in study vaccination.
- Unsolicited adverse events leading to hospitalization.

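### Protocol sections disagree on which unsolicited adverse events are collected, so events without a healthcare visit would be ascertained unevenly and would blur the all-AE and combined tables

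*Protocol*

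**What the plan says.** Several places set a narrow scope. Protocol 3.1 states: "All medically-attended unsolicited AEs and AEs leading to premature withdrawal will be collected", with SAEs as a separate item. The primary safety endpoints in 8.1.1.1 name the same categories, from Day 1 to Visit 6. The Time and Events Table has rows for these categories and none for other unsolicited events. Section 5.5, for children who complete the study, provides for an interview "to collect any medically attended adverse events, AEs leading to withdrawal, SAEs".

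Two places are wider. Section 5.5.1, otherwise close to a parallel list for children who leave early, puts "unsolicited adverse events occurring within 30 days of vaccination" ahead of the same three categories. No other section uses a 30-day window for adverse events. Section 5.3.1, which applies to days 331 and 661, says the parent or guardian "will be interviewed to determine if any unsolicited adverse events occurred", and events reported there go on the Adverse Events CRF.

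The analysis text is unrestricted. Protocol 8.4.2.1.3 says "This analysis applies to all adverse events occurring during the study" that are recorded on the AE CRF, and plans summaries of all reported and of at least possibly related events. SAP 13.3 says "All the unsolicited adverse events occurring during the study" will be recorded and grouped by system organ class and preferred term (SOC/PT), then lists eight analysis categories. SAP 13.4 combines solicited and unsolicited events, including a non-serious version for registry posting.

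The full protocol text available is version 1. The described changes in later versions do not touch this point, and SAP 13.3 and 13.4 read the same in both SAP versions.

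**The concern.** A percentage of children with an adverse event means something only if every child was asked the same question. Here the question depends on how the child left the study and on which section the site followed. A mild event that never led to a healthcare visit would be sought from a child seen under 5.5.1. It would not be sought from a completer seen under 5.5, but it would be from the same completer if the site followed 5.3.1.

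The planned all-reported, vaccine-related and combined tables then take whatever is on the AE CRF. No section limits them to the categories sought from everyone. Because the study has a single arm, those percentages are themselves the result, and part of what they show would be the questioning rather than the vaccine.

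**Working it through.** **1. Sections side by side**

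| Place | Applies to | Unsolicited events sought |
|---|---|---|
| Protocol 3.1, 8.1.1.1 | all children | attended, withdrawal, serious |
| Protocol 5.5 | completers, day 661 | attended, withdrawal, serious |
| Protocol 5.3.1 | clinic visits, days 331 and 661 | any |
| Protocol 5.5.1 | early terminators | any within 30 days of a dose, plus attended, withdrawal, serious |
| Protocol 8.4.2.1.3, SAP 13.3 text, SAP 13.4 | analysis | all recorded |

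Sections 5.3.1 and 5.5 give different scopes for the same day 661 visit. The three core categories appear in every collection row or fall within it. Only events outside them are exposed.

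**2. How many children might fall under 5.5.1**

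The plan's own figure (Protocol 8.5) is 135 enrolled for about 100 evaluable at 25% drop-out. Check: 100 / (1 − 0.25) = 133.3, rounded up to 134, against 135 stated, so it reproduces. Early terminators: 0.25 × 135 = 33.75, about 34.

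**3. What a pooled percentage estimates**

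Let e be the share of children asked the wider question, m the proportion with at least one core-category event, and a the proportion with at least one event of any kind. Then:

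pooled = e·a + (1 − e)·m

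This exceeds m by e(a − m) and falls short of a by (1 − e)(a − m). The documents give neither m nor a. With assumed m = 30% and a = 50%:

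- e = 25%: 0.125 + 0.225 = 35%, which is 5 points above m and 15 below a.
- e = 10%: 0.05 + 0.27 = 32%, which is 2 points above m and 18 below a.

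The pooled figure estimates neither quantity.

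**4. Range of the excess over the narrow-scope rate**

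Let q be the assumed chance that an early terminator reports a non-attended event within 30 days of a dose (20% to 40%). Let s be the share of those children already counted through a core category, taken as independent. Then excess = e × q × (1 − s).

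- No overlap, e = 25%: 34 × 0.20 = 6.8 and 34 × 0.40 = 13.6 children; divided by 135, 5.0% and 10.1%.
- s = 60%, e = 25%: 0.25 × 0.40 × (0.20 to 0.40) = 2 to 4 points.
- s = 60%, e = 10%: 0.10 × 0.40 × (0.20 to 0.40) = 0.8 to 1.6 points.

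All three lines assume that every early terminator has a termination visit and that completers are not asked the wider question. Relaxing either shrinks the excess. The range is not a bound: an assumed m = 30% and a = 80% at e = 25% would give 0.25 × 0.50 = 12.5 points.

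**The case against.** Much of the case against a serious problem stands.

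- **A reader might infer that the primary safety endpoint is compromised.** It is not. Medically attended, withdrawal and serious events are sought under both 5.5 and 5.5.1.
- **A reader might infer that the SAP reports a line for any unsolicited event.** The category list in SAP 13.3 has none, and its related non-serious category is already limited to attended events. The exposure comes from the protocol's all-reported-AE summary, the general SOC/PT text of SAP 13.3, and SAP 13.4. The separate table list is not part of the documents available.
- **A reader might infer a clean split between early leavers and completers.** The text does not establish one. Under 5.3.1 completers may be asked about any event. Section 5.5 includes a review of systems, which 5.1.2 defines as a structured interview about complaints. Section 3.4.2 sends newly described verbal reports to the AE CRF for any child. What is established is that sites have conflicting instructions.
- **The size may be small.** Section 5.5.1 procedures are done only when possible, some children will be lost to follow-up, and a child with an attended event adds nothing further to a subject-level percentage.
- **There is one arm and no hypothesis test**, so no between-group comparison is biased.

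None of this removes the contradiction. If 5.3.1 governs, it conflicts with 3.1, 5.5 and 8.1.1.1; if it does not, 5.5.1 stands alone. Either way the all-AE and combined tables lack a defined scope.

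**Conclusion.** The concern holds in limited form. Protocol 5.3.1 and 5.5.1 contradict 3.1, 5.5 and 8.1.1.1 on which unsolicited events are collected, and the analysis text does not filter out the difference. The damage is confined to events outside the three core categories, and therefore to the all-reported and vaccine-related SOC/PT summaries and the combined tables.

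The size is unknown. About 1 to 10 percentage points is an illustration resting on assumed values: an early-termination share of 10% to 25%, a non-attended event rate of 20% to 40%, and overlap with attended events of 0% to 60%. The top of the range needs all 34 expected drop-outs to attend a termination visit with no overlap, so it should not be quoted as an expected effect. The correction is worth making because it is cheap and the tables cannot be read properly without it.

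**What to change.** **Collection.** Reconcile Protocol 5.3.1 and 5.5.1 with 3.1, 5.5 and 8.1.1.1, so that every child is asked for the same categories over the same window.

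**Analysis.** In Protocol 8.4.2.1.3 and SAP 13.3 and 13.4, base the main SOC/PT and combined unsolicited summaries on the categories collected from all subjects. Keep solicited events that continue beyond day 7, which Protocol 7.1.1 requires on the AE CRF and SAP 13.3 combines with unsolicited events. Tabulate every other recorded event, including those judged vaccine-related, in a separate table labelled as not systematically collected. Merely listing these events would be a mistake, because non-attended events judged related to the vaccine would no longer be counted, contrary to Protocol 8.4.2.1.3.

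**Cost.** Wording in a few sections, one extra table, and slightly narrower questioning at early termination. If collection has already begun, the analysis change alone would still make the tables interpretable.
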